## 9.4.6. Tertiary/exploratory Analysis

Except if otherwise specified, no formal statistical testing will be conducted for tertiary / exploratory endpoints. Only the descriptive statistics will be computed. These analyses will be described in the SAP.

#### 9.4.7. Safety Analyses

All safety analyses will be computed on the Safety Analysis Set.

Adverse events will be coded using the most current version of the Medical Dictionary for Regulatory Activities (MedDRA) and tabulated by system organ class, preferred term, and treatment group for the number of AEs reported and the number and percentage of participants reporting each AE.

A by-participant AE data listing including onset and resolution dates, verbatim term, preferred term, blinded treatment, severity, relationship to treatment, action taken, and outcome will be provided.

Other safety data, including laboratory evaluations (biochemistry, haematology, coagulation, cardiac enzymes, thyroid function, and urine analysis), vital signs assessments, physical examinations, 12-lead ECG and spirometry will be summarized by time of collection and by treatment group. In addition, change from baseline will be summarized for vital signs and clinical laboratory results.

The frequency of participants with abnormal safety laboratory results will be tabulated by treatment.

#### 9.4.8. Pharmacokinetic Analysis

Blood PK analysis for SAB-176 will be performed using HAI and neutralisation assays against the H1N1 strain at each participant collection time point. This analysis will be conducted at both hVIVO and Sponsor designated laboratories.

PK parameters of interest may include:

Cmax, AUC0-t, AUC0-∞, tmax, t1/2

Pharmacokinetic parameters will be calculated using non-compartmental methods. Parameters will be summarised descriptively.

Exploratory nasal PK analysis may be performed, and parameters may be summarised descriptively.

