## 2.1. Background

Influenza causes substantial morbidity and mortality worldwide despite available antivirals and vaccines. Influenza is responsible for 226,000 excess hospitalizations and 30,000 to 50,000 deaths each year in the United States (US) alone (Thompson et al. 2003). Effective therapeutics are needed to prevent mortality or morbidity in those afflicted with severe influenza. Human plasma (delivered as Fresh Frozen Plasma units) or human intravenous immunoglobulin (hIVIg) with anti-influenza antibodies have been proposed as treatments for severe influenza (Luke et al. 2006). A limitation with plasma or hIVIg is that large numbers of human plasma donors/units must be screened to identify those few with a higher-than-average haemagglutination inhibition (HAI) titer to multiple strains of influenza. However, recent clinical trials have not shown benefit to hospitalized patients with severe Type A influenza infections treated with human-derived anti-influenza plasma or hIVIg (Beigel et al. 2019, Davey et al. 2019).

SAB Biotherapeutics, Inc., has developed SAB-176 to address the production limitations and lack of clinical efficacy of human-derived plasma or hIVIg. SAB-176 is a unique anti-influenza hIgG containing fully human polyclonal IgG antibodies with extremely high HAI and microneutralization titers against past, current, and potentially future strains of Type A influenza (H1N1/H3N2) and both lineages of Type B influenza (Yamagata/Victoria). SAB-176 is purified from the plasma of immunized Tc bovines that were immunized with a quadrivalent recombinant HA protein vaccine produced in insect cells. The HA antigens match the four influenza strains recommended yearly for the Northern hemisphere by the Center for Disease Control and Prevention.

Furthermore, Tc bovine hIgGs have an IgG1 subclass content of approximately 80-90% versus approximately 60% for human derived IVIg. IgG1 strongly activates complement and effector cells (natural killer cells, neutrophils, monocytes, etc.) of the innate immune system. SAB-176 is therefore much different than human-derived anti-influenza hIVIgs. SAB Biotherapeutics, Inc. believes that SAB-176's distinct attributes, in combination with early treatment of severe influenza disease, could demonstrate that the product reduces morbidity and mortality in patients with Type A and/or B influenza.

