#### 8.16.2. Challenge Virus Serology Samples

A participant must be serosuitable to take part in the study, i.e., he/she must have no or low pre-existing serum levels of antibodies specific to the Challenge virus. This antibody titre cut-off for serosuitability will be described in the AP.

Serum levels of pre-existing Virus specific antibodies to the Challenge virus will be determined using HAI influenza or as described in the AP.

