#### 8.16.3. Pharmacokinetic Blood Samples

Blood samples for determination of SAB-176 serum concentrations will be collected as outlined in the pharmacokinetic (PK) sampling schedule below:

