#### Sampling schedule:

Day 1 (IMP / placebo administration day): one sample pre-infusion and one sample at 1-hour post-infusion end (infusion end includes any time required for flushing), and at Days 2, 4, 6, 8, and 28.

The allowable time windows for the sampling are as follows:

- $\pm 5$  minutes from the scheduled time for time points  $\leq 1$ -hour post-infusion end.
- Allowable time windows from the scheduled time for time points >1-hour post-infusion end:
  - Day 2 timepoint (24 hours after infusion end): ±1 hour window.
  - $\circ$  Day 4 timepoint (72 hours after infusion end): ±2 hours window.
  - $\circ$  Day 6 timepoint (120 hours after infusion end): ±2 hours window.
  - $\circ$  Day 8 timepoint (168 hours after infusion end): ±2 hours window.
  - Day 28 timepoint (648 hours after infusion end): ±2 days window.
- There is no time window requirement for the pre-infusion sample. The pre-infusion PK sample must be taken on the same day prior to infusion.

Blood samples will be transported, processed, and stored in accordance with the AP. Pharmacokinetic analysis will be performed using HAI and neutralisation assays against the H1N1 strain at each participant collection timepoint. This analysis will be conducted at both hVIVO and Sponsor designated laboratories.

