# 10.6.2. Study definition of infection and illness

TERM	CRITERIA (RESPIRATORY SYNCYTIAL VIRUS, HEART RATE VARIABILITY AND INFLUENZA STUDIES)			
Seroconversion	A ≥4-fold increase in Virus specific antibodies from baseline to follow-up post-quarantine			
The following definitions should only be applied to data collected from Day 1 onwards				

TERM	CRITERIA (RESPIRATORY SYNCYTIAL VIRUS, HEART RATE VARIABILITY AND INFLUENZA STUDIES)
Lower Respiratory Tract Illness	
 
Any one of the following signs and/or symptoms on two consecutive scheduled assessments, at least one of which must feature Grade 2 severity, or if any of the following attain Grade 3 severity once: 
 
Self-reported symptoms: cough, shortness of breath, chest tightness and wheeze.
 
Physician findings: Abnormal breath sounds externally (e.g., stridor, wheezing) and on chest auscultation (rhonchi, crepitations or other).
 

Upper Respiratory Tract Illness	
 
Any one of the following signs and/or symptoms on two consecutive scheduled assessments, at least one of which must feature Grade 2 severity, or if any of the following attain Grade 3 severity once: 
 
Self-reported symptoms: rhinorrhoea (runny nose), nasal congestion (stuffy nose), sore throat, sneezing.
 
Physician findings: nasal discharge, otitis, pharyngitis, sinus tenderness.
 
 
 

Systemic Illness	Fulfils the criteria for febrile illness, or fulfils the definition of upper respiratory tract illness and/or lower respiratory tract illness and any one of the following symptoms on two consecutive scheduled assessments, at least one of which must feature Grade 2 severity, or if any of the following attain Grade 3 severity once: • malaise • headache • muscles and/or joint ache • chilliness • feverishness.
Febrile Illness	Any occurrence of temperature $\geq$ 37.9°C (confirmed by a repeat measurement as $\geq$ 37.9°C within 20 to 60 minutes).

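### SAB-176 pharmacokinetics are read as anti-H1N1 titre in participants challenged with H1N1, so the Day 28 sample, and with it half-life and AUC0-∞, mixes infused antibody with the participant's own response

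*Combined protocol and SAP*

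**What the plan says.** Section 8.16.3 gives the purpose of the samples: "Blood samples for determination of SAB-176 serum concentrations will be collected". The sampling schedule in that section then names the assay: "Pharmacokinetic analysis will be performed using HAI and neutralisation assays against the H1N1 strain at each participant collection timepoint". Section 9.4.8 repeats it: "Blood PK analysis for SAB-176 will be performed using HAI and neutralisation assays against the H1N1 strain at each participant collection time point". The parameters that may be derived are Cmax, AUC0-t, AUC0-∞, tmax and t1/2, by non-compartmental methods, summarised descriptively.

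Samples are taken before infusion, one hour after infusion end, and on Days 2, 4, 6, 8 and 28. The last is given as "Day 28 timepoint (648 hours after infusion end"), which is 27 days. Nothing is drawn between Day 8 and Day 28.

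Every participant is inoculated with A/California/2009 H1N1 on Day 0 and infused on Day 1 (section 6.1). Table 1 puts the chance of infection at about 65%, and section 2.3.2 accepts that participants may develop some immunity. At entry, by section 8.16.2, "he/she must have no or low pre-existing serum levels of antibodies specific to the Challenge virus"; that titre is measured by HAI or as the Analytical Plan describes. Section 2.1 credits the product with "extremely high HAI and microneutralization titers against past, current, and potentially future strains of Type A influenza (H1N1/H3N2").

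Section 10.6.2 defines seroconversion as an at least 4-fold "increase in Virus specific antibodies from baseline to follow-up post-quarantine". Note k to the Schedule of Activities places those samples at Day -2/-1 and Day 28.

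**The concern.** An HAI or neutralising titre measures anti-H1N1 activity from any source. The protocol reads that activity as drug concentration in 8.16.3 and 9.4.8, and as host response in the seroconversion definition. Both readings apply to serum drawn at Day 28.

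That sample is the only late one. It has most of the leverage on the terminal slope, and it is the point from which AUC0-∞ is extrapolated. No drug-specific assay, subtraction of endogenous titre, placebo-based correction or separate handling of infected participants is stated. The PK Analysis Set in section 9.3 is not limited to the SAB-176 arm either.

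At stake is the half-life and total exposure reported for a passive antibody. An inflated half-life would make the product look longer-lasting than it is, and later work could carry the figure forward.

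**Working it through.** The plan states no figure for this point, so there is none to reproduce. The existence of the bias follows from the assay and the schedule; its size is shown over a range.

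**Inputs from the protocol.** Day 8 is 168 h and Day 28 is 648 h after infusion end (8.16.3), so the interval is 480 h = 20 days. Infection is about 65% (Table 1) with 30 per arm (9.2): 0.65 × 30 = 19.5 infected in the SAB-176 arm, if treatment does not change infection.

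**Assumptions.** The documents give neither the half-life nor the titres. I take a true half-life T of 14, 21 or 28 days, mono-exponential decline, and a host titre at Day 28 equal to a fraction x of the drug titre still present, with none at Day 8.

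**Step 1: half-life from the Day 8 to Day 28 slope.** The observed ratio of the two titres is 0.5^(20/T) × (1 + x), so

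apparent t1/2 = 20 × ln 2 / −ln[0.5^(20/T) × (1 + x)].

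Example with T = 21 and x = 0.5: 0.5^(20/21) = 0.517; × 1.5 = 0.775; −ln 0.775 = 0.255; 13.86 / 0.255 = 54 days.

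| Host titre as share of remaining drug titre | T = 14 | T = 21 | T = 28 |
|---|---|---|---|
| 10% | 15.5 | 24.5 | 34.7 |
| 25% | 18 | 32 | 51 |
| 50% | 24 | 54 | 155 |
| 100% | 47 | no decline | no decline |

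Decline vanishes once 1 + x reaches 2^(20/T), that is, at a host contribution of about 169%, 94% and 64% for T = 14, 21 and 28.

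**Step 2: a log-linear fit to the last three samples (5, 7 and 27 days after infusion), with absolute titres.** AUC0-∞ is trapezoidal plus extrapolation. For T = 21 days:

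| Titre at infusion end | Host titre at Day 28 | Apparent t1/2 (days) | AUC0-∞ / true |
|---|---|---|---|
| 1280 | 40 | 23.5 | 1.11 |
| 1280 | 160 | 33.9 | 1.51 |
| 320 | 40 | 33.9 | 1.51 |
| 320 | 160 | not estimable | not estimable |
| 80 | 40 | not estimable | not estimable |

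At 320 with host titre 40, a true half-life of 14 days appears as 22.3 (AUC ratio 1.45) and one of 28 days as 48.0 (1.62). With no host titre the method returns the true half-life and AUC ratios of 1.01 to 1.03, so the excess comes from the host antibody.

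**Step 3: AUC0-t.** If t is Day 28, the last trapezoid spans 20 days, so a host titre of 40 adds 0.5 × 20 × 40 = 400 titre-days. Against a true AUC0-∞ of 320 × 21 / ln 2 = 9,695, that is 4%. Most of the inflation in AUC0-∞ therefore comes from the extrapolation.

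**Step 4: the reverse contamination.** The share r of infused titre left 27 days after infusion is 2^(−27/T): 7%, 26%, 41% and 51% for T = 7, 14, 21 and 28. An uninfected SAB-176 participant meets the 4-fold rule from infused antibody alone if the infusion adds P times the baseline titre with 1 + P × r ≥ 4, so P ≥ 3/r: 43.5, 11.4, 7.3 and 5.9.

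**The case against.** The best defence is that little hangs on this. PK is not among the objectives or endpoints in section 3, the parameters are ones that may be derived, and they are only summarised. That stands, and it limits the point to descriptive PK.

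The size is also assumed. With product titres as high as section 2.1 claims, a small host fraction is plausible; at 10% a true 21 days appears as 24.5. That stands too, which is why the low end is shown.

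A correction could sit in the SAP or the Analytical Plan, to which the protocol defers detail. It cannot be excluded. But 9.4.8 itself names assay, parameters and method and mentions no correction, and in 8.16.3 the Analytical Plan is cited only for transport, processing and storage.

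Four stronger readings are tempting, and the documents do not support them:

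- A reader might infer that a between-arm comparison of seroconversion is spoiled. None is planned. Seroconversion is a definition and a sampling note; it is absent from section 3 and Table 6, and laboratory-confirmed infection rests on viral shedding alone.
- A reader might infer that exposure becomes confounded with outcome. No exposure-response analysis is planned, and section 8.21 says that pharmacodynamic parameters are not evaluated. Greater bias with stronger infection is plausible but not shown.
- A reader might take section 10.6.2 to predict a 4-fold rise. It only defines the term, in a table shared with other virus studies.
- A reader might reject all H1N1-titre PK. Samples to Day 8 are probably less affected, and Cmax and tmax change only if a later titre exceeds the post-infusion peak.

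**Conclusion.** The point holds for descriptive PK. As sections 8.16.3 and 9.4.8 are written, t1/2 and AUC0-∞, and AUC0-t where t is Day 28, include the participant's own anti-H1N1 antibody. In infected participants who respond, the values are too high or cannot be computed.

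The direction needs only that the host response adds to the titre by Day 28 and contributes less at Day 8. The size needs a half-life and a host-to-drug ratio that the documents do not give: over host contributions of 25% to 100%, a true 14 days appears as 18 to 47 days, and a true 21 or 28 days runs from 32 or 51 days to no decline at all.

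In the SAB-176 arm, infused antibody alone can meet the 4-fold seroconversion rule. That matters only if seroconversion is reported. The primary and secondary efficacy conclusions do not depend on any of this. The text should be changed, but the trial's main result is not at risk.

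**What to change.** In section 9.4.8, and in the SAP to match:

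1. Compute H1N1-titre PK parameters in the SAB-176 arm from samples through Day 8 only: Cmax, tmax and AUC to Day 8. Five post-dose samples remain (one hour, Days 2, 4, 6 and 8), so the PK Analysis Set rule of at least three post-dose results can still be met.
2. Drop t1/2 and AUC0-∞ derived from the H1N1 titre.
3. Report Day 28 as total anti-H1N1 titre by arm, beside the placebo titres. Placebo participants are sampled on the same schedule, so their titres show the size of the host response and also whether any of it is present by Day 8.
4. If seroconversion is reported, add that infused antibody alone can satisfy the rule in the SAB-176 arm.

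The cost is wording, with no new samples. Section 8.16.3 makes no distinction by arm, so placebo sera should already be assayed; if the laboratory meant to skip them, they would have to be run. What is lost is a terminal half-life, which this assay cannot validly give here.

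If a terminal half-life is wanted, HAI against a non-challenge component of the quadrivalent product (H3N2 or a B lineage) on the same sera is an option. It needs an extra assay and a correction for the pre-infusion titre, because the entry limit on antibody covers only the challenge virus. It is not part of the core fix.

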# 9.5. Interim Analyses

No interim analysis (i.e., an analysis of early trial data, before enrolment is completed, to detect trends that might warrant modification of the protocol, change in data being collected or trial termination) is planned for the study.

# **10.** Supporting Documentation and Operational Considerations

# 10.1. Appendix 1: Regulatory, Ethical, and Study Oversight Considerations

#### 10.1.1. Regulatory and Ethical Considerations

- This study will be conducted in accordance with the protocol and with the following:
  - Consensus ethical principles derived from international guidelines including the Declaration of Helsinki and Council for International Organizations of Medical Sciences International Ethical Guidelines
  - Applicable International Council for Harmonisation (ICH) Good Clinical Practice (GCP) Guidelines
  - Applicable laws and regulations
- In addition to regulatory submission, the protocol, protocol amendments, ICF, Investigator's Brochure, and other relevant documents (e.g., advertisements) must be submitted to an REC by the Investigator and reviewed and approved by the REC before the study is initiated.
- Any amendments to the protocol will require REC approval before implementation of changes made to the study design, except for changes necessary to eliminate an immediate hazard to study participants.
- The Investigator will be responsible for the following:
  - Providing written summaries of the status of the study to the REC annually or more frequently in accordance with the requirements, policies, and procedures established by the REC.
  - Notifying the REC of SAEs or other significant safety findings as required by REC procedures.
  - Providing oversight of the conduct of the study at the study site and adherence to requirements of ICH guidelines, the REC, European regulation 536/2014 for clinical studies (if applicable), and all other applicable local regulations.

#### **10.1.2.** Financial Disclosure

Investigators and sub-Investigators will provide the Sponsor with sufficient, accurate financial information as requested to allow the Sponsor to submit complete and accurate financial certification or disclosure statements to the appropriate regulatory authorities. Investigators are responsible for providing information on financial interests during the course of the study and for 1 year after completion of the study.

#### **10.1.3.** Informed Consent Process

The Investigator will obtain a signed study specific ICF from each participant before any study specific procedures are performed.

When historical screening data collected through the hVIVO Generic Screening process is used for screening, the study specific ICF will be obtained at quarantine admission (Day -2 / -1) from each participant before any study specific procedures are performed.

Potential participants will typically be sent a copy of the ICF when their Screening Visit / Quarantine admission visit (as applicable) is arranged and at least a day prior to the visit and will be encouraged to

read it prior to their appointment. Upon arrival at the Screening Visit / Quarantine admission visit (as applicable), the ICF is discussed by the Investigator, and they will be given the opportunity to ask any questions and may take the information sheet away to consider their participation.

All participants will be required to have a good understanding of English and the Investigator will be responsible for ensuring that the participant understands the information contained in the ICF. Once the Investigator has confirmed that the participant has understood the study, including the benefits and risks of participation, the participant and the Investigator can sign and date the ICF.

The ICF must be signed and dated by the participant and countersigned by the Investigator (whoever conducted the consent discussion). A copy of the ICF will be given to the participant, and the original will be held in the hVIVO TMF.

Participants will be assured that they can withdraw from the study at any time and for any reason without prejudice to their future medical care, and that they will be informed in a timely manner if new information becomes available that may affect their willingness to continue their participation in the study. This information will be included within in the ICF.

The ICF will contain a separate section that addresses the use of samples for future research. The Investigator or authorised designee will explain to each participant the objectives of the exploratory research. Participants will be told that they are free to refuse to participate and may withdraw their consent at any time and for any reason.

Participants may be given the option to take part in a separate ethically approved exploratory non-interventional trial that aims to collect physiological data which will require them to wear a wearable device via an additional informed consent, which will be separately ethically approved (for further details see Section 8.10).

#### 10.1.4. Data Protection

Participants will be assigned a unique identifier by hVIVO. Any participant records or datasets that are transferred to the Sponsor will contain the identifier only; participant names or any information which would make the participant identifiable will not be transferred.

The participant must be informed that his/her personal study-related data will be used by the Sponsor in accordance with local data protection law. The level of disclosure must also be explained to the participant in ICF.

The participant must be informed that his/her medical records may be examined by Clinical Quality Assurance auditors or other authorized personnel appointed by the Sponsor, by appropriate REC members, and by inspectors from regulatory authorities.

#### **10.1.5.** Committees Structure

This study will not include an early safety data review. However, participant safety will be continuously monitored by the Sponsor's internal/external safety review committee which includes safety signal detection at any time during the study.

### 10.1.6. Dissemination of Clinical Study Data

The key design elements of this Protocol will be posted on publicly accessible registers, such as ClinicalTrials.gov. Where required, protocol summaries will also be posted on national or regional clinical trial registers or databases (e.g., EudraCT database) in compliance with the applicable regulations.

It is the Sponsor's (or Sponsor delegate) responsibility to send the Clinical Trial Summary Report to the REC and MHRA (if required) within 1 year of the end of the trial. In addition, the Sponsor or Sponsor delegate is responsible for entering appropriate data into the EudraCT results database within 1 year of the end of the trial.

The PI/Investigator shall provide assurance to participants that their confidentiality will be maintained hVIVO have a legal obligation to protect at all times the confidentiality of participant personal data from the point of capture, through processing, dissemination in line with consent from the participant and to its final disposition.

